10.2.1. Adverse Events of Special Interest

AESIs include the following:

- Periodontitis/gingivitis
- Hyperkeratosis
- Serious infections
- Pneumonia

AESIs will be identified by the entries in the corresponding eCRF pages.

Hyperkeratosis TEAESIs will be summarized by location and signs. Dental (periodontitis / gingivitis) will be summarized by PT and by the outcome of the Investigator evaluation. Serious infections will be summarized by body system and PT. Pneumonia will be summarized by symptoms / laboratory findings and PT.

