#### **7.1.3. Participant Discontinuation/Withdrawal From the Study**

A participant may decide to withdraw from the study at any time, for any reason, without prejudice to subsequent care or treatment by the Investigator. When this occurs, the participant should complete all the procedures for the Early Discontinuation Visit. Participants who discontinue the treatment due to AEs should remain under observation until the resolution or stabilization of the AEs. A participant may be discontinued from the study drug treatment before completion for any of the following reasons:

1. Participant death
2. Participant experiences an AE(s)/SAE(s) that warrants discontinuation, as judged by the Investigator and/or Insmmed Medical Director
3. A major protocol deviation, which in the opinion/discretion of the Investigator and/or Insmmed, compromises the data integrity of the study
4. Participant is noncompliant with the study drug treatment (defined as <80% compliance after at least 2 reeducation efforts)
5. Withdrawal by participant
6. Termination of the study by the Sponsor
7. Investigator discretion
8. Participant lost to follow-up
9. Participant pregnancy
10. Skin events ([Section 8.2.7.1](#))
11. Periodontal criteria met ([Section 8.2.7.2](#))

12. Diagnosis of a malignancy during study, excluding carcinoma in situ of the cervix, or squamous or basal cell carcinoma of the skin
13. Serious infection ([Section 8.2.7.3](#)), defined as any infection (other than associated with a PE) that:
  - Requires parenteral treatment with an antibiotic requiring admission to the hospital or parenteral treatment with an antifungal, antiviral, antiparasitic, or antiprotozoal agent
  - Is an opportunistic infection, such as TB or other infection whose nature or course may suggest an immunocompromised status
  - If a participant requires oral antibiotics to treat acute pulmonary symptoms, pneumonia, or any other infection, discontinuation/withdrawal from the study will be determined by the Investigator
14. Participants who develop neutropenia defined as ANC  $<1000/\text{mm}^3$
15. Participants who develop any of the stopping rules for liver safety defined in [Section 10.6](#).

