### 8.2.7.3. Other Infections

Participants will be monitored throughout the study for potential infections. Severe infections, such as any infection requiring treatment with parenteral antibiotics/antiviral/antifungal agent, any clinical endoparasitosis, any opportunistic infection, should be reported as AESIs. Generally, all uncommon, atypical, peculiar, or unusually persistent infections should be reported as AESIs.

Pneumonia will be a specific subcategory that will be monitored through the study.

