#### **10.1.8. Committees Structure**

An SRC will be chartered, comprising:

- Insmmed Vice President of Pipeline Programs
- Insmmed Medical Monitor for Brensocatic Clinical Development Program
- Insmmed Clinical Pharmacology Expert
- Vice President, Drug Safety and Pharmacovigilance (or designee)
- Principal Investigator for the study
- And possible external expert consultants

Participant safety will be continuously monitored by the Sponsor, which includes safety signal detection at any time during the study. After the first 3 cohorts (brensocatic 10, 25, and 40 mg QD) have completed the study, the SRC will review available data (PK and safety data [vital signs, clinical laboratory test values, ECGs, and AEs]) from all cohorts to determine if brensocatic has shown an acceptable safety and PK profile, and whether the brensocatic dose should be escalated to 65 mg QD as planned.

In particular, the SRC will review the following events:

- Any deaths, regardless of causality
- AESIs, including hyperkeratosis, periodontal/gingival events, and infection

Complete details can be found in the SRC charter.

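### SAP 10.2.1 narrows the protocol's infection AESI to undefined serious infections plus pneumonia, without declaring the change, so some protocol-defined infection AESIs have no category summary of their own

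*SAP*

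**What the plan says.** Protocol 8.2.7 names three AESI groups, one of which is infection. Protocol 10.1.8 uses the same broad term for the Safety Review Committee: "AESIs, including hyperkeratosis, periodontal/gingival events, and infection".

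Protocol 8.2.7.3 gives the content of the infection group in three parts:

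- Severe infections: "Severe infections, such as any infection requiring treatment with parenteral antibiotics/antiviral/antifungal agent", together with clinical endoparasitosis and opportunistic infection.
- A general limb: "Generally, all uncommon, atypical, peculiar, or unusually persistent infections should be reported as AESIs".
- A subcategory: "Pneumonia will be a specific subcategory that will be monitored through the study".

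SAP 10.2.1 opens its list with "AESIs include the following" and gives four entries: periodontitis/gingivitis, hyperkeratosis, serious infections and pneumonia. For infection it plans two displays. One is "Serious infections will be summarized by body system and PT"; the other shows pneumonia by symptoms or laboratory findings and PT. Cases are found by this rule: "AESIs will be identified by the entries in the corresponding eCRF pages". The SAP does not say what makes an infection serious.

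SAP Section 2 says that the SAP prevails where it differs from the protocol and that differences will be detailed in the CSR. SAP Section 13 reports no change from the protocol-specified analyses and mentions only the added Screened Analysis Set.

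**The concern.** Protocol 2.3.2 lists infections among the key risks expected from DPP1 inhibition and says they will be monitored as AESIs. The AESI displays are where a reader will look for that risk by dose. If the SAP applies a narrower filter than the protocol's reporting instruction, investigators may report events as infection AESIs that the analysis then has no row for.

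The term used is also unsettled. Protocol 8.2.7.3 speaks of severe infections, and Protocol 10.3.3 warns that severe and serious are different things. The SAP itself uses severe infection in 5.1, serious infections in 10.2.1 and plain infections in 11.1.4. An undefined filter on a small safety category should be fixed before treatment assignments are known, so that the choice cannot follow the data.

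**Working it through.** The plan gives no figure to reproduce; the check is a mapping of definitions.

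**Step 1. Possible meanings of serious infection.**

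- Reading A, the SAE criteria in Protocol 10.3.2: death, life-threatening, hospitalisation, disability, important medical event and so on.
- Reading B, Protocol 7.1.3 item 13, which defines serious infection for discontinuation and cross-refers to 8.2.7.3. It leaves out infections associated with a pulmonary exacerbation (PE). It counts parenteral antibiotics only where hospital admission is required, but parenteral antifungal, antiviral, antiparasitic or antiprotozoal treatment without that condition. A further limb is "Is an opportunistic infection, such as TB or other infection whose nature or course may suggest an immunocompromised status". The last bullet of item 13, on oral antibiotics, leaves withdrawal to the investigator; I read it as a decision rule, not as part of the definition.

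**Step 2. Apply both readings to events that Protocol 8.2.7.3 makes AESIs.** Unless stated, assume that the event is not pneumonia, not PE-associated, not opportunistic or suggestive of immunocompromise, and meets no SAE criterion other than the one described.

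| Event | A | B | Own infection AESI summary in SAP 10.2.1? |
|---|---|---|---|
| Parenteral antibiotic, admitted to hospital | yes | yes | yes |
| Pneumonia | n/a | n/a | yes, pneumonia display |
| Opportunistic infection, not admitted | no | yes | depends on reading |
| Parenteral antiviral or antifungal, not admitted | no | yes | depends on reading |
| Parenteral antibiotic, PE-associated, admitted | yes | no | depends on reading |
| Parenteral antibiotic, not admitted | no | no | **none** |
| Clinical endoparasitosis, no parenteral treatment | no | no | **none** |
| Unusually persistent or atypical infection | no | no | **none** |

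Three event types have no infection-specific AESI summary on either reading, and three more depend on a choice that the SAP does not make. The setting without admission is not fanciful here: Protocol Section 2 describes intravenous antibiotic treatment at home as well as in hospital.

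**Step 3. Where these events would still appear.** SAP 10.2 tabulates TEAEs by SOC and PT, also by severity and by relationship to IP, and lists all AEs. Its overall summary has a row for participants with at least one TEAESI. Entry to that row follows the eCRF rule. The eCRF (dated 17 Aug 2022 in SAP Section 2) is reproduced in neither document, so inclusion can be neither confirmed nor ruled out.

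**Step 4. Size.** The documents give no rate for these events, so the number affected is an assumption. In a dose group of about 7 (SAP Table 1), 0, 1 or 2 affected participants are 0/7 = 0%, 1/7 = 14.3% or 2/7 = 28.6%. In the CFTR modulator stratum of about 5, one participant is 1/5 = 20%.

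**The case against.** The strongest reply is that the SAP's term is the protocol's own. Protocol 7.1.3 defines serious infection with a pointer to 8.2.7.3, and its limb on infections suggesting an immunocompromised status would take in many atypical or persistent infections without any SAE criterion. This stands in part: on that reading the gap is smaller. But the SAP does not cite the definition, and the definition still leaves out parenteral antibiotics without admission, PE-associated infections, and persistent infections that do not suggest immunocompromise. Protocol 8.2.7.3 makes none of these exceptions.

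Four stronger conclusions might be inferred, and the documents do not support them:

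- *These infections fall outside every AESI summary.* Not shown. The SAP list is introduced with a non-exhaustive verb, the overall table has an any-TEAESI row, and the eCRF that feeds it cannot be inspected.
- *Serious pneumonia is double-counted.* The protocol makes pneumonia a subcategory, so overlap is by design. The SAP gives the two groups different displays and does not add them, and the any-TEAESI row counts participants with at least one event.
- *The exposure-safety analysis is distorted.* SAP 11.1.4 sends it to a separate PK/PD Analysis Plan and uses the broad term infections. Nothing makes 10.2.1 its input.
- *The milder, earlier form of the risk is missed.* Neither document describes atypical or persistent infections as an early stage of serious infection.

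It is also fair to say that this is descriptive reporting without hypothesis tests, and that the primary safety endpoint, TEAE incidence, is unaffected. That limits the consequence but does not close the definitional gap.

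**Conclusion.** The point holds as a definitional mismatch. SAP 10.2.1 replaces the protocol's infection AESI with a narrower and undefined category, takes precedence in doing so, and does not declare the change. Section 2 promises that differences will be detailed in the CSR, but that helps only if someone has recognised this one. Infection AESIs that are serious on neither reading, and are not pneumonia, have no category-specific AESI summary; their place in the any-TEAESI count is unknown.

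The practical effect is an infection AESI display that may undercount by dose relative to the protocol's definition. A single participant moves a dose group's row by about 14 percentage points, if such an event occurs at all. This rests on two assumptions: that serious carries one of the two protocol meanings, and that no eCRF instruction redefines it. No adverse event is lost from safety reporting and the trial's validity is not threatened. It is a cheap correction that should be made before database lock and unblinding.

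**What to change.** In SAP 10.2.1:

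1. Define the category as infections per Protocol 8.2.7.3, summarised by body system and PT.
2. Show serious infections and pneumonia as sub-rows, state which definition of serious applies, and add an infection total that counts each participant once.
3. State which eCRF entries identify these events, including those that are neither serious nor pneumonia.

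If the narrower scope is intended, define serious infections in 10.2.1, declare and justify the narrowing in Section 13, and say where the remaining protocol infection AESIs will be shown.

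The cost is SAP wording and one revised table. The one thing to check first is whether the existing eCRF pages capture the wider group; the documents do not show this.

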10.2.2. Deaths

A listing of all deaths (from the eCRF “Death details”) including AEs resulting in death will be provided.

10.3. Clinical Laboratory Evaluations

For the general layout of the tables see [Section 7.1](#).

Continuous laboratory tests (hematology, clinical chemistry, and coagulation) will be summarized using descriptive statistics at scheduled visits (Screening, baseline, and EoT [Day 28 or Early Discontinuation]) for observed values and changes from baseline.

Shift tables (i.e., low-normal-high at baseline versus low-normal-high at EoT in a 3-by-3 contingency table) will be provided to assess changes in laboratory values from baseline to last visit with respect to the reference range. Reference ranges established by the central laboratory will be used to determine the categories. Values below the lower limit (LL) of the reference range will be classified as “low”. Values above the upper limit (UL) of the reference range will be classified as “high”. Values within the reference range will be classified as “normal”.

Clinical laboratory results will be provided in participant listings.

Participants experiencing alanine aminotransferase or aspartate aminotransferase $\geq 3 \times$ upper limit of normal (ULN) and total bilirubin $> 2 \times$ ULN according to Hy's Law will be listed.

10.4. Vital Signs

Systolic and diastolic blood pressure, pulse, respiratory rate, oxygen saturation, temperature, height, and weight will be summarized by scheduled visits.

Descriptive summaries of observed values and absolute and percentage changes from baseline will be based on available data.

10.5. Electrocardiogram

ECG will be summarized by scheduled visits. ECG will be collected in triplicates. The mean of the triplicates will be summarized, and all measurements will be listed.

Descriptive summaries for the mean of the triplicate collections of the 12-lead ECG tracings for observed values and changes from baseline will be based on available data. Number and percentage of participants with ECG findings will be summarized by scheduled visit and timepoint for investigator and vendor interpretation.

Number and percentage of participants experiencing extraordinary ECG values will be summarized by visit:

- QTcF > 450 ms, QTcF > 480 ms,
- change from baseline in QTcF > 30 ms, change from baseline in QTcF > 60 ms.

10.6. Other Safety Assessments

10.6.1. Physical Examination

Any abnormalities noticed by the investigator during the Physical Examination at Screening will be recorded in the medical history, or as an AE if occurring or worsening after signing the informed consent form.

Dates of Physical Examination will not be listed.

10.6.2. Pregnancy

Pregnancy results will be listed for all participants with outcome.

11. PHARMACOKINETICS

Individual PK parameters of brensocatic will be determined by non-compartmental analysis (NCA) using Phoenix[®] WinNonlin[®] (WNL) version 8.2 or later (Certara L.P, Princeton, New Jersey). PK outputs will be prepared using SAS Version 9.4 or higher (SAS Institute, Inc., Cary, North Carolina). The primary PK endpoints are brensocatic C_{max} , t_{max} , and AUC_{0-24} after single dose administration on Day 1; and C_{max} , t_{max} , AUC_{0-24} , and $t_{1/2}$ after multiple dose administration on Day 28. Brensocatic plasma concentrations and PK parameters, including the ones that are not included in the primary endpoint, will be summarized as described in [Section 7.1](#). Statistical summary tables and mean plasma concentration by time figures will be presented based on the PK Analysis Set. Brensocatic plasma concentration by time figures for individual participants and listings will be based on the Safety Analysis Set. PK parameters will be listed for the PK Analysis Set.

Strategies for ICEs as outlined in [Section 3.1](#), [3.2](#), and [7.2](#) will be applied.

If calculable, the following PK parameters listed in [Table 5](#): will be determined for brensocatic in plasma following single oral dose administration (Day 1).

Table 5: Plasma PK Parameters After Single Dose Administration or First Dose Administration of Multiple Dose Study

Parameter	WNL Name	CDISC Name	Definition
C_{max}	Cmax	CMAx	Maximum observed plasma concentration
t_{max}	Tmax	TMAx	Time to C_{max}
t_{last}	Tlast	TLST	Time of the last measurable (positive) concentration
AUC_{0-24}	AUC0_24	AUC24	AUC from time T1=0 to T2=24 hours
AUC_{last}	AUClast	AUCLST	AUC from time T1=0 to T2=the last timepoint with measurable concentration

CDISC = Clinical Data Interchange Standards Consortium.

If calculable, the PK parameters listed in [Table 6](#) will be calculated for brensocatic in plasma following multiple oral dose administration after last dose administration (Day 28).

Reasons for PK parameters not calculable will be listed.

Table 6: Plasma PK Parameters after Multiple Dose Administration after Last Dose

Parameter	WNL Name	CDISC Name	Definition
C_{trough}	Ctrough	CTROUGH	Concentration at the end of a dosing interval [taken directly before next administration]; Obtained on Days 2, 14, 28 and 29

Parameter	WNL Name	CDISC Name	Definition
C_{\max}	Cmax	CMAx	Maximum observed plasma concentration in a dosing interval
C_{\min}	Cmin	CMIN	Minimum observed plasma concentration in a dosing interval
t_{\max}	Tmax	TMAX	Time to C_{\max}
t_{last}	Tlast	TLST	Time of the last measurable (positive) concentration
$t_{1/2}$	HL_Lambda_z	LAMZHL	Elimination half-life
λ_z	Lambda_z	LAMZ	Elimination rate constant
AUC_{0-24}	AUC0_24	AUC24	AUC from time T1=0 to T2=24 hours
AUC_{last}	AUClast	AUCLST	AUC from time T1= 0 to T2=the last timepoint with measurable concentration
AUC_{∞}	AUC ∞	AUCINF	AUC from time T1=0 to T2=infinity
CL/F	CLss_F	CLFTAU	Total clearance following oral administration
V_d/F	Vz_F	VZFTAU	Volume of distribution at terminal phase following oral administration
C_{av}	Cavg	CAVG	Average concentration over the dosing interval
$R_{\text{ac,AUC}}$	RacAUC*	ARAUC	Accumulation ratio calculated from AUC_{0-24} at steady state divided by AUC_{0-24} after single dosing
$R_{\text{ac,Cmax}}$	RacCmax*	ARCMAX	Accumulation ratio based on C_{\max} calculated from C_{\max} at steady state divided by C_{\max} after single dosing

* Obtained through additional calculations in WNL outside of NCA model.

11.1. Pharmacokinetic Analysis, Concentration, and Parameter Tables, Listings, and Figures, and Statistical Analysis of Pharmacokinetic Parameters for Final Analysis

Any anomalous PK plasma concentration values observed at pre-dose on Day 1 will be identified in the CSR and reported in listings. All pre-dose values (BLQ and any anomalous values) will be set to zero.

PK plasma concentrations that are collected outside the acceptable collection windows (Section 1.3.1, CSP) will be flagged in the listing with a footnote that these concentrations are excluded from the concentration summary.

11.1.1. Pharmacokinetic Concentrations

Concentration Listings:

Concentration listings will include nominal PK sampling time, actual sampling times relative to dose administration, deviation from nominal time, percent deviation from nominal time, and concentrations. Plasma concentrations below the lower limit of quantification (LLOQ) will be presented as BLQ in the listings and the LLOQ value presented as a footnote. Missing PK samples will be reported as no sample or not reportable as appropriate and considered excluded from PK analysis.

Concentration Summary Tables:

Source data as reported from the laboratory will be used for calculation of concentration summary statistics. Concentrations for brensocatib will be summarized by use of CF modulator, brensocatib dose level, day, and nominal timepoint. See [Section 7.1](#) for details of the statistics to be included.

For summary tables, all BLQs will be considered zero, and the number of BLQs and non-BLQs at each scheduled timepoint will be reported. Summary statistics will not be calculated if the number of non-BLQ concentrations at a scheduled timepoint is <3 and will be reported as not calculable (NC).

The rules followed for calculation and presentation of concentration data with regards to the number of decimal places/significant digits for the listings of participant level concentrations and summary tables of concentration are as follows:

Concentration Listings and Tables	Rounding
Individual Concentrations	n s.d. as supplied by bioanalytical laboratory
Minimum and Maximum	n s.d. capped at 4
Mean, SD, Median, GM	n+1 s.d. capped at 4
CV%, gCV%	1 d.p.
N, n	whole number

s.d. = significant digits, d.p. = decimal place.

Concentration Figures:

For arithmetic mean linear/linear graphs, all BLQ values will be substituted with zero for calculation of arithmetic mean and for log/linear graphs the mean of natural log transformed values will be displayed (this should not include zero).

For individual linear/linear and log/linear graphs all BLQ values will be substituted as follows:

- BLQ values on Day 1 pre-dose will be set to 0. When using log/linear scale, these values will be considered missing.
- BLQ values post-dose will be set to missing.

To visualize participant-level concentrations and the comparison between groups for each treatment, the descriptive PK graphs listed below will be generated. LLOQ will be given in a footnote.

- Individual participant profiles for plasma concentration data over time on linear/linear and log/linear scale (log scale for concentration data, time on linear scale), stratified by PK Day (Day 1 and Day 28).
- Mean (+ SD) profiles for plasma concentrations over time on linear/linear and log/linear scale (SD will only be displayed on linear/linear scale) by dose level overlaid in the same figure, for each PK Day [Day 1 and Day 28].
- Mean (+ SD) profiles for plasma trough concentrations (pre-dose values) over time from Day 2 to Day 29.

Figures will be generated using unique line style and marker for each plot in the graph. For all PK concentration-time plots, linear scale will be used for the x-axis (i.e., do not use an ordinal scale). Actual sampling time will be used for individual plots while scheduled sampling time will be used for mean plots.

11.1.2. Pharmacokinetic Parameters

PK parameters will be calculated by NCA methods from the concentration-time data as specified in beginning of [Section 11](#) following these guidelines:

- Actual time from dose will be used in the calculation of all derived PK parameters, except when parameters are calculated for safety/dose escalation meetings when nominal times may be used.
- There will be no imputation of missing data.
- Handling of BLQ samples for derivation of plasma PK parameters after single and multiple dose administration:
 - BLQs for Day 1 at the beginning of a participant profile (i.e., pre-dose and leading BLQs) will be set to zero.
 - BLQs between evaluable concentrations (embedded BLQs), will be set to missing before the calculation of the PK parameters.
 - Terminal BLQs (trailing BLQs at the end of participant profile) will be set to missing.

Participants with partial data will be evaluated on a case-by-case basis to determine if sufficient data are available for reliable estimation of PK parameters. PK parameters will be estimated according to the guidelines presented in [Table 7](#):

Table 7: PK Parameter and Estimation

Parameter	Guideline for Derivation
C_{max} , C_{min} , t_{max} , C_{trough} , t_{last} ,	Obtained directly from the observed concentration-time data

Parameter	Guideline for Derivation
AUC_{last}	
The AUC from zero time (pre-dose) to the time of last quantifiable concentration will be calculated by a combination of linear and logarithmic trapezoidal methods. Unless specifically requested and justified, the linear up/log down trapezoidal method will be employed for all AUC calculations.
 
The AUC_{last} is the sum of areas up to the time of the last quantifiable sample:
 $AUC_{last} = \int_0^t C_{last} * dt$
AUC_{0-24}	
The AUC from zero time to the specific time x is the sum of areas up to the specific time x sample, where x=actual time at 24h:
 $AUC_{0-x} = \int_0^x Cx * dx$ 
If the PK sample at 24h is collected out of time window, AUC_{0-24} and its related parameters will be flagged in the listing but included in the analysis.

AUC_{∞}	
The area from zero time extrapolated to infinite time (AUC_{∞}) will be calculated as follows:
 $AUC_{\infty} = AUC_{0-last} + C_{last}/\lambda_z$ 
where C_{last} is the last observed quantifiable concentration.

λ_z and $t_{1/2}$	
 The terminal phase first-order rate-constant (λ_z) will be estimated. A minimum number of three data points in the terminal phase will be used in calculating λ_z with the adjusted correlation coefficient (R^2 adjusted) ≥ 0.8. Otherwise, λ_z will be considered not calculable, and all the λ_z dependent parameters (i.e., $t_{1/2}$, CL/F, and Vd/F) will be flagged in listings and excluded accordingly from summary tables and statistical analysis of PK parameters. The reason for exclusion will be listed/footnoted in parameter listings. Unless otherwise determined by PK Scientist's best knowledge and judgment, the interval used to determine λ_z should be equal or greater than 1.5-fold the estimated $t_{1/2}$, and if less than 1.5-fold, λ_z will be flagged in listings and might be excluded (based on sponsor specific requirements) from summary tables and statistical analysis of PK parameters. All the derived parameters (i.e., $t_{1/2}$, CL/F, and Vd/F) may also be flagged in listings and excluded from statistical analysis of PK parameters. The reason for exclusion will be listed/footnoted in parameter listings. The $t_{1/2}$ will be calculated as follows: $t_{1/2} = \ln 2 / \lambda_z = 0.693 / \lambda_z.$
CL/F	
Following extravascular (e.g., oral) administration, apparent systemic clearance of parent drug following steady state administration will be calculated from:
 $CL/F = \frac{Dose}{AUC_{0-24}}$ 
The administered brensocatib dose will be used for the calculation.

V _d /F	
Volume of distribution at terminal phase following either intravascular or extravascular dosing after steady state administration may be calculated from:
 $V_d/F = \frac{Dose}{\lambda_z * AUC_{0-24}} = (CL/F) / \lambda_z$

Parameter	Guideline for Derivation
C_{av}	Average concentration at steady state (Day 28) will be calculated as $C_{av} = AUC_{0-24}/24$
R_{ac}	Accumulation ratio, calculated from comparison of single dose and steady state data: $R_{acAUC} = \text{Steady state } AUC_{0-24} / \text{Single dose } AUC_{0-24}$ $R_{acC_{max}} = \text{Steady state } C_{max} / \text{Single dose } C_{max}$

PK Parameters Listings:

PK parameters will be listed by participant. PK parameters that will be flagged and/or excluded from summary tables and statistical analyses of PK parameters will be flagged and footnoted with the reason for flagging/exclusion.

The Phoenix NCA core output will be provided as a Word document.

PK Parameter Summary Tables:

Biostatistics group will consider the derived PK parameters as source data and will use this data without rounding for calculation of PK parameters summary statistics tables.

PK parameters will be summarized as specified in [Section 7.1](#).

The rules followed for presentation of PK parameters data with regards to the number of decimal places/significant digits for the listings of participant level PK parameters and summary tables of PK parameters are as follows:

Table 8 Presentation of PK Parameters in Tables and Listings

PK Parameter Tables and Listings	Rounding
Derived Individual Parameters	3 s.d.
Directly Derived Individual Parameters (C_{max} , C_{trough} , C_{min})	n s.d. as supplied by the analytical laboratory but not more than 3 s.d.
Minimum and Maximum	3 s.d.
Mean, SD, Median, GM	3 s.d.
CV%, gCV%	1 d.p.
Comparative Estimates (e.g., Ratios)	3 d.p.
CI and Percentages	2 d.p.
p-Values	4 d.p.
N/n	whole number
Exceptions for PK Tables	
t_{max} Individuals, and Minimum, Maximum	2 d.p.
t_{max} Median Only	2 d.p.

s.d. = significant digits, d.p. = decimal place

PK Parameter Figures:

Steady state will be assessed based on determination of individual half-lives. Dose-proportionality plots are described in the following section.

